## Justification, Objective, & Research Design

**If you uploaded a separate research protocol document in the 'Research Protocol' page, cite the applicable section and page numbers from that document in the answer boxes below.**

**1 \* Describe the purpose, specific aims, or objectives of this research. State the hypothesis to be tested:**

This study will evaluate the ethical, legal and social impacts of patients receiving genetic results and will assess whether providing free genetic testing in a very convenient manner (in-home, saliva collection) will improve uptake of cascade testing.

The objectives of the protocol are to: (Aim 1) evaluate the uptake of cascade screening and preventative therapies before and after the implementation of a simplified screening process and (Aim 2) assess proband and family member perspectives about the return of research results and cascade screening for the KCNQ1 Thr224Met variant. We will conduct a mixed methods study in the Old Order Amish community where the KCNQ1 variant is enriched over 100,000-fold compared to other populations. The intervention will offer free, saliva-based genetic testing for family members of probands. The rate of uptake of testing and preventative therapy will be compared before (i.e. when 'traditional' \$50 blood-based testing was available to family members) and after the intervention is implemented (i.e. when 'simplified' free, in-home, saliva-based testing was available).

Aim 1 - The primary outcome is the rate of uptake of cascade screening before ('traditional') versus after ('simplified') the intervention. The secondary outcomes include: extent of disclosure of genotype results to family members before and after the intervention, proportion of informed relatives who get screened before and after the intervention, and the uptake of appropriate preventative care (e.g. seeing a cardiologist and/or taking beta-blocker). The tertiary outcomes are demographic characteristics associated with uptake of cascade screening or uptake of preventative therapy.

Aim 2 - We will also assess qualitative themes surrounding the return of results process and cascade screening using interviews.

**2 \* Discuss the research design including but not limited to such issues as: probability of group assignment, potential for subject to be randomized to placebo group, use of control subjects, etc.:**

This study will use mixed methods to evaluate the rate of uptake and impact of cascade screening and preventative therapies for carriers of the KCNQ1 mutation before and after our intervention. Our intervention will offer free, saliva-based cascade screening for first-degree family members of probands.

Aim 1: Prior to the start of our intervention, all probands will be mailed a consent letter describing the study, a questionnaire, a response card and a copy of the family invitation letter. The questionnaire will capture data on the period of time since their return of results, including, the extent to which they shared results with family members, health behaviors (i.e. are they taking preventative therapy, if indicated) and how the results have impacted them. With the proband's permission, invitation letters will be mailed to their first degree relatives to offer study participation including the intervention (free, in-home, saliva-based genetic testing) and completion of questionnaires about their experiences with genetic testing. The proband can decide to enroll their minor children who still live at home in the cascade screening (Screening only for children under age 18 with specified consent/assent). We will offer the intervention for approximately 9 months, then we will repeat the mailed questionnaires assessing uptake, disclosure, health behaviors, and general impact of the intervention.

We will compare outcomes before the implementation of our intervention (the 'traditional' cascade screening period) and after (the 'simplified' cascade screening period). Our primary outcome addresses the question of whether our simplified cascade screening intervention improves uptake of screening. Our secondary outcomes assess whether, with access to simplified screening (1) probands will tell more family members, who may or may not choose to get screened, (2) informed family members are more likely to get tested, and (3) identifying more individuals with the KCNQ1 variant actually results in more beta-blocker prescriptions since the Amish typically take very few prescription medications. The tertiary outcomes are demographic characteristics associated with uptake of cascade screening or uptake of preventative therapy.

Aim 2: Over the course of the intervention, in-depth interviews will be conducted in a subset of 30 probands and 45 family members in order to assess their perspectives on receiving the results and undergoing cascade screening. All family members who have been contacted by a proband will be eligible regardless of mutation carrier status and whether or not they chose to get screening. We will enroll approximately 15 probands who shared their genetic results with a family member, 15 probands who did not share, 15 family members who were screened and are mutation positive, 15 family members who were screened and were mutation negative, and 15 family members who did not undergo screening. All interviews will be audio recorded and transcribed. Transcripts will be imported into NVivo software. Interview data will be analyzed using a combined deductive and inductive approach. Questions from the interview guide will be used to develop an initial coding scheme, and inductive codes will be added as transcripts are reviewed and additional themes are noted. The first set of transcripts (N=5) will be initially independently coded by two members of the research team to develop a consensus coding scheme. Once the coding scheme is being applied consistently, one member of the research team will code the remaining transcripts. These data will be independently reviewed by two other research team members and interviews will be halted when the entire research team agree that informational redundancy has been reached. In sum, our interviews will assess how the ROR process impacted participants, how cascade screening impacted participants, why or why not participants chose to undergo screening, what were the barriers to undergoing screening, and why or why not participants followed recommendations for beta-blocker therapy.

These interviews will assess patient-reported impact of disclosure and impacts on health behaviors. They will also inform our understanding of why cascade screening of family members is or is not initiated and the extent to which cost and ease of testing (blood versus in-home saliva collection) impact screening uptake. By comparing rates of cascade screening before and after our intervention together with qualitative interviews, we can evaluate the extent to which ease, comfort, transportation issues, and cost impact the uptake cascade screening and improve our ability to apply the findings to appropriate comparable situations in clinical practice and in the most optimized manner.

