To date, 88 individuals have participated in a return of results study (ROR) for clinical confirmation of the mutation, collection of clinical information, genetic counseling, and recommendations for treatment. Genetic counseling included recommendations for all first degree relatives (who are at 50% risk of having the KCNQ1 mutation) to undergo genetic screening (cascade testing). This testing would involve going to the Clinic for Special Children and obtaining the genetic test via a blood sample for \$50 per test.

Cascade testing is considered to be a highly efficient procedure for identifying additional mutation carriers who might be helped through a preventive intervention. Despite the very clear potential clinical benefit of cascade testing, uptake has traditionally been low, particularly in the United States where active screening (i.e. direct contact of relatives) is not allowed due to privacy laws.

Understanding the impact of returning these results and initiating cascade screening of family members is critical for developing best practices and optimizing the processes. Most cascade screening studies to date have been conducted outside the United States where different laws exist regarding contacting family members. Therefore, our study will attempt to address a gap in knowledge regarding whether overcoming physical and financial barriers will improve uptake of cascade screening.

**4 \*Provide the scientific or scholarly background, rationale, and significance of the research and how it will add to existing knowledge:**

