**1 \* Provide the rationale and sample size calculations for the proposed target population:**

Our study is based on 88 KCNQ1 Thr224Met probands who were identified as part of another research study and chose to undergo clinical confirmation of their genotype and clinical evaluation for long QT syndrome. We cannot approach probands who chose not to undergo the return of results process. These 88 probands have over 700 first degree family members who may be eligible for cascade screening with our intervention. We can assume some of the family members have died and some may not live in Lancaster County, but a very large proportion will be eligible for testing. Due to privacy laws we cannot approach a family member without permission from the proband. With permission from the proband, we will send family letters or we will provide family letters to probands for them to share with family members. This study will compare the rate of uptake of cascade screening before and after our intervention of a simplified cascade screening program. Given that an individual who undergoes cascade screening before our intervention, during the 'traditional' period does not need to undergo testing again, we cannot statistically compare the difference in the proportion of family members who undergo cascade screening before and after the intervention or the statistical power that our study will have to detect a difference in uptake. That being said, our experience suggests that uptake of cascade screening will be very low among the Amish during the 'traditional' phase when cost, transportation, and an invasive test are barriers. This pilot study will test whether we can overcome these barriers and detect a meaningful improvement in uptake of cascade screening, disclosure to family members, and uptake of appropriate medical intervention. We will define this meaningful improvement a priori as a 15% improvement. For example, if we have 3% of eligible individuals undergo cascade screening during the traditional phase, we would deem 18% of eligible individuals getting tested a clinically meaningful increase. This would translate into 15/500 getting tested before our intervention and 87/485 getting tested after implementing our intervention. Another way of looking at this is that approximately 2-3 probands would initiate cascade screening before the intervention and 12-13 would after the intervention (assuming 7 children per proband).

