Our primary outcome is the rate of uptake of cascade screening before ('traditional') versus after ('simplified') the intervention. Uptake for this outcome is defined as the proportion of first degree family members (i.e. offspring and siblings) of the initial 88 probands who undergo cascade screening out of all eligible first degree family members (as defined by the Fisher book). We will compare the proportion before versus after the simplified screening approaches. Any individuals who undergo screening before the intervention will no longer be eligible for screening with the simplified cascade screening so the denominator will decrease accordingly. We have chosen to use the denominator of all first degree relatives defined by the Fisher book because this number is not dependent on participants returning the surveys where they will provide information on how many family members they told (and how many they have). Our secondary outcome includes the proportion of informed relatives who get screened. The number of participants screened for all outcomes will be obtained from charts (as [name] is ordering physician for all tests).

Our secondary outcomes are:

- Extent of disclosure of genotype results before and after the intervention. This outcome is defined as the number of family members (siblings and children) told (reported via survey) out of the total number of proband first degree relatives (known from the Fisher Book and asked on the survey).
- Proportion of informed first-degree relatives who get screened before and after the intervention. This outcome is defined as the number of family members tested out of the number told by probands (reported via surveys)
- The overall rate of uptake of preventative therapy among probands and family members (e.g., see a cardiologist and/or take a beta-blockers)

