## Recruitment

1 \* Describe plans for recruitment, including the identification of potential participants (or acquisition of charts/records/samples) and initial interactions with them: (If this study involves the VA please list all sites at which recruitment will take place.):  
Individuals who participated in the KCNQ1 ROR study (probands) and their first degree blood-related family members will be invited to participate. First degree family members of identified carriers will also be eligible for testing.

All probands who underwent the return of results process (n=88 to date) will be mailed an information / consent letter and response form (uploaded in Informed Consent Section), a questionnaire about their attitudes and experience with genetic testing (uploaded to Surveys Section), and a sample family invitation letter (uploaded below). These participants all agreed to recontact during the consent process for the study their KCNQ1 ROR was conducted under (see Retrospective Data Section). In the information/consent letter, probands will be asked to complete and return the questionnaire as an indication that they agree to join the study. They will be informed that they may be asked to participate in an in-person interview. The letter will also ask if we can invite their adult first-degree family members who live locally to take part in the study, whether or not the proband participates. They will be given the option to enroll their minor children (with appropriate consent and assent) in the free cascade testing portion of the study. The proband will complete and return the response form to indicate whether they agree to contact of family members.

With the proband's permission, the family invitation letter will be mailed to the first-degree family members of the proband using information from the 2009 Fisher Book and 2018 Address book of the Lancaster County Amish. At the proband's request, copies of the family invitation letter will, instead, be mailed to the proband so they can hand deliver them to family members of their choosing. The family invitation letter will explain our intervention offering free, mail-in, saliva testing of first degree family members.

2 \* Describe measures that will be implemented to avoid participant coercion or undue influence (if not applicable to the study, enter "N/A"):

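### The primary comparison sets raw uptake over a traditional period of unstated length against an offer of about 9 months, with no counting cut-off and no adjustment for time

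*Combined protocol and SAP*

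**What the plan says.** **Periods.** Justification, Objective, & Research Design, item 1, separates the periods by which test was on offer. The simplified side is the time "after the intervention is implemented (i.e. when 'simplified' free, in-home, saliva-based testing was available". Item 2 (Aim 1) gives the order of events: "Prior to the start of our intervention, all probands will be mailed a consent letter", and later "We will offer the intervention for approximately 9 months, then we will repeat the mailed questionnaires".

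**Start of the traditional period.** Under item 3, traditional testing follows from each proband's return of results: "Genetic counseling included recommendations for all first degree relatives" to be tested. The baseline questionnaire in item 2 also looks back to that date. Results were returned over time; Recruitment, item 1, describes the group as "All probands who underwent the return of results process (n=88 to date". No length is given for this period.

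**Outcome.** Sample Size and Data Analysis, item 2, and SAP B1.1 define uptake as the number screened over all eligible first-degree relatives in the Fisher book, and compare the two proportions. One adjustment is made between periods: "Any individuals who undergo screening before the intervention will no longer be eligible for screening with the simplified cascade screening", and the denominator shrinks to match. Tests are counted from charts, because one co-investigator "is ordering physician for all tests". No closing date for the count is stated.

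**Criterion.** Sample Size and Data Analysis, item 1, and SAP A1 say that the two proportions cannot be compared statistically, and then state: "We will define this meaningful improvement a priori as a 15% improvement". The example of 3% rising to 18% shows that percentage points are meant.

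**The concern.** A cumulative proportion grows with the time over which events are counted. Two such proportions can be compared directly only if they cover similar time, or if time is adjusted for. Here one side covers an unknown time that differs from proband to proband, and the other covers about 9 months with an end that is implied but not fixed for the chart count.

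Three errors are possible, and they do not all run the same way:

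- Traditional time longer than 9 months gives the old approach more time to collect tests, so the raw difference understates the gain.
- Traditional time shorter than 9 months gives it less, so the raw difference overstates the gain.
- Counting tests ordered after the offer closes raises the after-proportion through time alone, and also overstates the gain.

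Because the plan sets aside a formal test, the 15-point rule is its only stated criterion for a meaningful improvement. An open counting date also leaves a choice that could be made after the data are seen.

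**Working it through.** **Inputs.** The figures 500 relatives, 3% and 18% come from Sample Size and Data Analysis, item 1, and SAP A1. The 9-month offer comes from Research Design, item 2. The traditional length T is not in the documents, so every value of T below is an assumption. The largest, 36.6 months, is the span of existing data in Retrospective Data, item 1 (10/12/2015 to 10/31/2018, 1,115 days); it is not labelled as the traditional period.

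**Step 1: reproduce the example.** 0.03 × 500 = 15. 500 − 15 = 485. 0.18 × 485 = 87.3, so 87. Then 15/500 = 3.00%, 87/485 = 17.94%, and the raw difference is 14.94 points. The example reproduces and, apart from rounding, sits on the 15-point rule. It carries no unit of time.

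**Step 2: put both sides on 9 months, assuming a constant testing rate.** The 9-month equivalent of 3% over T months is 1 − 0.97^(9/T). The standardised difference is 17.94% minus that. The ratio of testing rates is [−ln(1 − 87/485)/9] ÷ [−ln(0.97)/T].

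| Assumed T (months) | Traditional uptake at 9 months | Difference (points) | Rate ratio |
|---|---|---|---|
| 3 | 8.73% | 9.2 | 2.2 |
| 6 | 4.47% | 13.5 | 4.3 |
| 9 | 3.00% | 14.9 | 6.5 |
| 12 | 2.26% | 15.7 | 8.7 |
| 24 | 1.14% | 16.8 | 17.3 |
| 36.6 | 0.75% | 17.2 | 26.4 |

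The same raw result falls short of, meets or exceeds the rule according to a length that the plan does not give.

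**Step 3: drop the rate assumption where possible.** If every family had at least 9 months of traditional time, and a share f of the 15 tests fell in the first 9 months, the difference is 17.94 − 3.00f. That is 14.94 at f = 1, 16.44 at f = 0.5 and 17.94 at f = 0. In that case the raw figure understates the gain by 0 to 3.0 points. This bound does not cover families with less than 9 months.

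**Step 4: could some families have short traditional time?** The protocol counts 88 probands and the SAP 70. If 70 is the earlier count (an assumption), 88 − 70 = 18 probands joined later, and 18/88 = 20.5%. Their traditional time is not stated.

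**Step 5: late tests.** Each test counted after the offer closes adds 1/485 = 0.21 points. As illustrations, 5 add 1.03 and 10 add 2.06. One extra test takes the unrounded example past the rule: 88/485 = 18.14%, and 18.14 − 3.00 = 15.14.

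**The case against.** The strongest reply is that the periods are not really open. The offer lasts about 9 months and the questionnaires on uptake follow it, so the natural reading is a simplified period of about 9 months. The study is also a pilot that claims no test and no power, so the 15 points are a descriptive benchmark. Comparing cumulative uptake is a legitimate choice, and for traditional periods of 9 months or more the distortion in the example is at most 3 points.

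Much of this stands. The boundary between the periods is given, and a window of about 9 months is implied. What is missing is its extension to the chart count and any length for the traditional side. The benchmark is still set in advance and applied to the two proportions.

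A reader might infer more than the documents support:

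- **That the bias has a known direction.** It does not. Step 2 shows both directions, and the lengths needed to choose between them are absent.
- **That tests will be counted for 18 months because participation can last that long (Study Procedures, item 3).** That duration runs to the final questionnaire and is not a testing window. Under a constant rate, 17.9% at 9 months would become 32.7% at 18, but only if testing continued at the same pace for 9 months after the offer ended. Nothing in the documents says so.
- **That home visits without a reply (Informed Consent Process, item 2) show late counting.** That text says who may be visited and gives no timing.

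**Conclusion.** The point holds as a gap in definition with a possible exposure-time bias of undetermined direction. The plan as written compares cumulative proportions over unequal and partly unstated time. In its own example the 9-month-equivalent difference runs from 9.2 to 17.2 points, against a raw 14.9, for traditional lengths from 3 to 36.6 months; each late test adds 0.21 points. The range rests on an assumed constant testing rate and assumed lengths. It shows how far the result could move, and does not estimate how far it does.

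The effect would be larger if traditional uptake were above 3%. The point does not make the primary outcome unusable or show that the plan favours the intervention. It is a change that should be made, because it is cheap and the 15-point conclusion could turn on it.

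**What to change.** Add to Sample Size and Data Analysis, item 2, and to SAP B1.1:

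> Each test is assigned to a period by its order date. The traditional period for a relative runs from the proband's return of results (the earliest, if there is more than one proband) to the start of the intervention. The simplified period runs from the start of the intervention for about 9 months. Tests ordered after the offer closes are not counted in the primary outcome.

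Record the start and the close as dates, and say whether they are common to the study or set by family. The proband mailing is not a suitable start, since the protocol places it before the intervention.

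Keep the planned raw proportions in all eligible Fisher-book relatives. Report with them:

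- the length of each window (median, range);
- uptake per relative-month in each period;
- as a sensitivity analysis, uptake in the first 9 months after return of results against the 9-month offer, among relatives with at least 9 months of traditional time;
- whether the 15-point conclusion holds on the time-standardised scale.

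**Cost.** A few sentences, plus extraction of return-of-results, intervention-start and test-order dates; charts are already the source for tests. Late tests leave the primary count. Uptake per relative-month assumes a roughly constant rate. The sensitivity analysis leaves out families with short traditional time, so their number should be given. In it, relatives tested in the traditional period after month 9 count in neither numerator yet leave the simplified denominator. In the example this moves the after-proportion by at most 0.54 points (87/485 = 17.94% against 87/500 = 17.40%).
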